11.4 Vital Signs

Systolic blood pressure, diastolic blood pressure, pulse rate, respiratory rate, and body temperature at baseline and each of the post-baseline assessments will be summarized and presented using descriptive statistics. See Section 8.4.3 for the identification of the assessments used in the analyses. For each of the post-baseline assessments, change between baseline and that assessment in a specific vital sign will be calculated as follows,

$$\text{Change from baseline} = [\text{Vital sign at the post-baseline assessment}] - [\text{Vital sign at baseline}],$$

and will be summarized and presented using descriptive statistics. If a specific type of vital signs is missing at either baseline or a specific post-baseline assessment for a subject, change from baseline will be missing.

Maximum decrease and increase from baseline in systolic and diastolic blood pressure will be summarized separately using descriptive statistics, to assess the potential for defibrotide to cause peri-infusional hypotension.

Baseline and post-baseline values for each visit in Section 8.4.3 will be categorized as low, normal, or high and presented on a shift table based on the criteria listed in Table 4.

Table 4 – Vital Signs Normal Ranges

Parameter	Low	Normal	High
Systolic blood pressure	< 60 mmHg	≥60 and ≤160 mmHg	>160 mmHg
Diastolic blood pressure	<50 mmHg	≥50 and ≤100 mmHg	>100 mmHg
Pulse rate	<40 beats per min.	≥40 and ≤120 beats per min.	>120 beats per min.
Respiratory rate	<10 breaths per min.	≥10 and ≤40 breaths per min.	>40 breaths per min.
Temperature	<36 degrees Centigrade	≥36 and ≤39 degrees Centigrade	>39 degrees Centigrade

The following summaries will be provided:

- Summary of vital signs
- Summary of maximum decrease and increase from baseline in systolic and diastolic blood pressure
- Shift table of vital signs results from baseline

The following listings will be provided:

- Listing of vital signs

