### 6.8.3 Vital Signs

Vital signs will include blood pressure, pulse, respiratory rate, and body temperature. The method for measuring body temperature (e.g., oral, tympanic, rectal, or axillary) is to be recorded. For all patients, vital signs will be recorded during screening, once daily from baseline through Day+30 post-HSCT or hospital discharge, whichever is sooner; twice weekly after early hospital discharge until Day +30 post-HSCT (if applicable); weekly between Days +31 and +60 post-HSCT; and at the Days +100 and +180 post-HSCT visits. For patients who develop VOD during the study and are administered rescue defibrotide, vital signs will be recorded daily from diagnosis of VOD through hospital discharge, twice weekly through resolution of VOD, 30 days after the last dose of rescue defibrotide, and at the Days +100 and +180 post-HSCT visits.

More intensive vital signs monitoring will be conducted on the first day of defibrotide dosing, which occurs on:

- the day before the first day of the conditioning regimen for patients in the DP arm who receive defibrotide prophylaxis and
- on the first day of defibrotide administration for patients in the BSC arm who receive defibrotide treatment for VOD

For this intensive monitoring, vital signs will be recorded at pre- dose, at 15, 30, 60, and 120 minutes ( $\pm 5$  minutes) following start of infusion and at 15 minutes ( $\pm 5$  minutes) following the end of the first and second infusions.

Defibrotide (JZP-381)  
Clinical Trial Protocol: 15-007 Version 4.0

Jazz Pharmaceuticals, Inc.  
20 August 2018

If patients in the DP arm who receive defibrotide prophylaxis receive rescue defibrotide for the treatment of VOD, intensive vital signs monitoring will be conducted only on the first day of defibrotide prophylaxis regardless of when they move into the rescue arm.

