#### **9.14.3 Vital Signs Results**

For vital signs, descriptive statistics (n, mean, standard deviation, median, minimum, and maximum) will be summarized by study phase and treatment received during the Prophylaxis Phase. Changes from baseline to maximum decrease in systolic and diastolic blood pressure will also be summarized. Abnormal vital signs (to be defined in the SAP), the number and percentage of patients with any postbaseline vital sign results above and/or below specified levels, and summary statistics (i.e., mean, median, minimum, maximum, standard deviation, and number of patients) will be presented by study phase and treatment received during the Prophylaxis Phase for each vital sign as per protocol schedule.

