- c. Patients who develop clinical signs and symptoms of VOD after discharge from the hospital must be monitored twice weekly instead of weekly through Day +60 post-HSCT. If these patients are diagnosed with VOD per the modified Seattle criteria, they will begin treatment for VOD and follow the schedule of events in [Appendix 2](#).
- d. If the twice weekly visit falls within the window of the Day +30 post-HSCT visit, the Day +30 post-HSCT assessments should be performed at that visit.
- e. Eligibility must be confirmed before randomization.
- f. Randomization of patients should be the last screening activity performed.
- g. Prior medications include those current at the time of screening through baseline, all prior therapies for the malignant disease, conditioning regimen for HSCT, and GvHD prophylaxis. Review of planned conditioning regimen for GvHD prophylaxis to ensure that the eligibility criteria will continue to be met.
- h. Complete physical examination, including assessments of the skin, head, eyes, ears, nose, throat, neck, thyroid, lungs, heart, abdomen (with palpation of the liver and with measurement of abdominal girth for pediatric patients), lymph nodes, extremities, and a general assessment (including edema). Height will be measured during screening only. Whenever possible, assessment of right upper quadrant pain will be performed.
- i. Vital signs include blood pressure, pulse, respiratory rate, and body temperature. For the DP arm, intensive monitoring of vital signs will be recorded during the first and second infusion of defibrotide on the first day of defibrotide dosing (within 24 hours before the first dose of the conditioning regimen). For this intensive monitoring, vital signs will be recorded at pre-dose, and 15, 30, 60, and 120 minutes ( $\pm 5$  minutes) following start of infusion and at 15 minutes ( $\pm 5$  minutes) following the end of the first and second infusions.
- j. Clinical laboratory tests include serum chemistry (ALT, albumin, alkaline phosphatase, AST, BUN, calcium, chloride, creatinine, glucose, magnesium, phosphorus, potassium, sodium, total bilirubin [direct and indirect], total protein, CrCl [using the Cockcroft-Gault formula for adults and Schwartz formula for pediatric patients] and if cystatin C is measured, then GFR [using the Grubb or Larsson formula]); hematology (hemoglobin, hematocrit, MCV, WBC count with differential, platelet count); and coagulation (aPTT, INR).

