8.3 Study Phase

In this study, the occurrence of VOD and the administration of rescue defibrotide represent a clinical landmark time point for safety. Therefore, for the safety analyses, 2 study phases are defined with respect to the administration of rescue defibrotide, as follows:

- **Prophylaxis Phase:**
 - If VOD occurs, the prophylaxis phase starts on the Baseline date and ends on the day before the start date of rescue defibrotide (ie, rescue treatment start date – 1).
 - If VOD does not occur, the prophylaxis phase starts on the Baseline date and ends on the date of study completion/early termination.
- **Rescue Treatment Phase:**
 - For the subset of subjects who developed VOD and received rescue defibrotide, the rescue treatment phase begins on the start date of rescue defibrotide and ends on the date of study completion/early termination.

The start date of rescue defibrotide will be derived as the date of the first administration of defibrotide on or after the investigator diagnosis of VOD.

Unless otherwise noted, safety summaries will be reported by study phase and by treatment received during the Prophylaxis Phase.

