8.4.3 Vital Signs

Intensive vital signs recorded during the first and second infusion of defibrotide on the first day of defibrotide dosing will be summarized at the nominal visit and time recorded in EDC. The analysis windows for all other visits will follow Table 1 and Table 2 in [Section 8.4.1](#) for the prophylaxis and rescue phases, respectively.

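### The blood-pressure summary that the SAP ties to peri-infusional hypotension is not limited to infusion readings and is sampled unevenly between the arms

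*SAP*

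**What the plan says.** SAP 11.4 attaches a stated purpose to one blood-pressure measure. The largest drop and the largest rise since baseline, for each of the two pressures, "will be summarized separately using descriptive statistics, to assess the potential for defibrotide to cause peri-infusional hypotension". It gives no time window for that maximum. Protocol 9.14.3 plans the same measure, also without a window: "Changes from baseline to maximum decrease in systolic and diastolic blood pressure will also be summarized".

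The reporting period comes from SAP 8.3: "Unless otherwise noted, safety summaries will be reported by study phase and by treatment received during the Prophylaxis Phase". Without VOD, that section runs the Prophylaxis Phase from baseline to study completion or early termination, nominally Day +180.

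Two streams of readings fall in that phase:

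- **Routine, both arms** (Protocol 6.8.3): "once daily from baseline through Day+30 post-HSCT or hospital discharge, whichever is sooner". After early discharge they are twice weekly to Day +30, then weekly to Day +60, then at Days +100 and +180.
- **Intensive, DP arm only in this phase** (Protocol 6.8.3, 7.2.1.1 and Appendix 1, footnote i): "intensive monitoring of vital signs will be recorded during the first and second infusion of defibrotide on the first day of defibrotide dosing". Readings are taken pre-dose, at 15, 30, 60 and 120 minutes, and 15 minutes after the infusion ends.

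SAP 8.4.3, to which 11.4 refers, states that the intensive readings "will be summarized at the nominal visit and time recorded in EDC". All other vital signs follow the visit windows of SAP Tables 1 and 2.

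**The concern.** Peri-infusional vital signs are part of a stated secondary safety objective (Protocol 2.2). The only measure that the SAP links by name to infusion hypotension is an extreme value with no infusion window. Two distortions follow, in opposite directions:

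1. **False signal.** The minimum of a longer series is lower by chance, and only the DP series contains the intensive readings.
2. **Dilution.** Routine falls during transplant illness (sepsis, fluid shifts, other drugs) can set a patient's maximum, so the infusion contributes little or nothing.

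Neither a raised nor an unremarkable DP figure could then be read as evidence about infusion.

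**Working it through.** The documents give no target figure, power or variance for this summary, so there is nothing to reproduce. The check counts readings from the schedule and works out what the maximum does under stated assumptions.

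**Extra DP readings.** (4 during + 1 after infusion) × 2 infusions = 10, or 11 if the pre-dose reading of infusion 2 is counted.

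**Routine readings, both arms**
- In hospital to Day +30, with the protocol's 5 days of conditioning: 35 daily + 4 weekly + 2 late = 41.
- Discharge at Day +15: 20 daily + about 4 twice-weekly + 4 weekly + 2 late = 30.
- SAP Table 1 windows only: 11.

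**Assumptions, none from the documents**
- SD 12 mmHg per reading.
- Same-day correlation 0 or 0.5.
- True effect 0 or 10 mmHg at all ten infusion readings.
- Later routine pressure either at baseline or 10 mmHg below it.

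**Formula.** With independent readings and no effect, the mean maximum fall is SD × m(n), where m(n) is the expected maximum of n standard normals. The DP excess is 12 × [m(n+10) − m(n)]:
- n = 41: 12 × (2.257 − 2.171) = 1.0
- n = 30: 12 × (2.161 − 2.043) = 1.4
- n = 11: 12 × (1.889 − 1.586) = 3.6

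Simulation with 40,000 patients per arm gives 1.0, 1.4 and 3.7 for the same cases. The full grid, with ranges over the two correlations, in mmHg:

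| Routine readings | Later routine pressure | DP excess, no effect | Arm difference, true 10 mmHg effect |
|---|---|---|---|
| 41 | at baseline | 0.8–1.0 | 3.1–4.9 |
| 30 | at baseline | 1.0–1.4 | 3.7–5.9 |
| 11 | at baseline | 2.4–3.7 | 7.1–10.4 |
| 41 | 10 lower | 0.1 | 0.7–1.0 |
| 30 | 10 lower | 0.1–0.2 | 1.0–1.4 |
| 11 | 10 lower | 0.5–0.7 | 2.4–3.6 |

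In every row the mean change over the infusion readings themselves recovers the effect (0 without it, 10 with it).

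**A second assumed model** uses SD 9 mmHg between days and 9 within a day, 36 daily readings, and a 10 mmHg drop only at 30 and 60 minutes:
- Mean maximum fall without effect: BSC 26.9, DP 27.7.
- With effect: DP 29.1. The effect therefore adds 29.1 − 27.7 = 1.4 mmHg.
- Even with the effect, an infusion reading sets the maximum in only about 28% of DP patients, or about 9% if routine pressure later runs 10 mmHg lower.

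**The infusion-window maximum under that second model.** The largest fall from the same infusion's pre-dose value over five readings averages 9 × m(5) = 9 × 1.163 = 10.5 mmHg with no effect, and about 16.5 with it. It reveals about 6 of the 10 mmHg, but its null value is well above zero.

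**The case against.** The strongest reply is that the infusion effect already has its own display. SAP 8.4.3 summarizes the intensive readings by nominal time, and 11.4 applies change from baseline to each post-baseline assessment. SAP 7.1 includes the minimum and maximum among the default statistics, so the largest individual fall at each time point will be shown, and all vital signs are listed. This stands. A reader might infer that a real infusion effect would be hidden, or that the maximum is the only planned look at the question. The documents support neither. What the display lacks is each patient's largest fall across the time points. Falls at different times in different patients average out in the means. The shift table does not fill that gap, because it calls systolic pressure low only below 60 mmHg, so a fall from 120 to 75 stays normal.

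Three further points:

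- **The whole-phase window is inferred.** It comes from the SAP 8.3 default; 11.4 does not state it, and its reference to 8.4.3 could mean windowed readings only. That is why the working uses 41, 30 and 11 routine readings.
- **Baseline is already close to pre-dose for infusion 1.** SAP 8.2.2 takes the last value on or before the first dose. This stands for infusion 1 in the DP arm, but not for infusion 2.
- **An infusion-window maximum is also inflated by chance and has no BSC comparator.** This stands, and it limits how the added measure may be read.

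A reader might also conclude that the comparison is simply biased against defibrotide. The extra readings push that way, but dilution pushes the other way, and the balance depends on values that the documents do not give.

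**Conclusion.** The point holds as a mismatch between a measure and its stated purpose. The maximum fall in SAP 11.4 is not restricted to infusion readings and, read with SAP 8.3, draws on at least 10 more readings in the DP arm than in the BSC arm. Under the assumed SD of 12 mmHg, chance inflation of the DP figure ranges from 0.1 to 3.7 mmHg. The arm difference for a true 10 mmHg effect ranges from largely masked (0.7) to fully visible (10.4). These ranges rest on assumed variances, correlations and illness course, so the reliable conclusion is that the result cannot be interpreted, not that it errs in a known direction. Because no test is planned on this summary and the time-point means remain available, the severity is minor to moderate.

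**What to change.** In SAP 11.4:

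1. Define the peri-infusional measure, in defibrotide recipients, as each patient's largest fall from the same infusion's pre-dose reading among the 15, 30, 60 and 120 minute readings and the reading 15 minutes after the end, for infusions 1 and 2 separately. Present it beside the mean changes by time point. Note that a maximum over several readings exceeds zero by chance, that BSC has no matching readings, and that the pre-dose value of infusion 2 may carry over an effect of infusion 1.
2. State which readings enter the between-arm maximum decrease. Restrict it to routine scheduled readings common to both arms over the same window, leaving out the intensive readings, and drop the claim that it addresses peri-infusional hypotension.

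The cost is SAP wording and some programming on data already collected. No procedure, efficacy endpoint or alpha allocation changes. The limitation is that the added measure describes defibrotide recipients only and cannot by itself separate a drug effect from chance variation.

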## 4 SELECTION OF STUDY POPULATION

Adult and pediatric patients scheduled to undergo HSCT who are at high risk or very high risk of developing VOD will be enrolled in the study.

A total of 400 patients from approximately 100 enrolling study sites in countries throughout the world, including the US, are planned. If DMC recommends an increase in sample size after the interim analysis, an increase in sample size up to a maximum of 600 patients total will be implemented.

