### 4.1 Inclusion Criteria

Each patient must meet the following criteria to be enrolled in this study. Study treatment is defined as defibrotide prophylaxis in addition to BSC or BSC alone.

1. Patient must be above the age of 1 month as of Study Day 1 (as defined in [Section 3.1](#)).
2. Patient must be scheduled to undergo allogeneic (adults or pediatric patients) or autologous HSCT (pediatric patients only) and be at high risk or very high risk of developing VOD.
  - a. High-risk patients must meet both of the following criteria (i and ii):
    - i. Patient must be scheduled to receive myeloablative conditioning, defined as either of the following:
      - a. At least 2 alkylating agents (e.g., cyclophosphamide, busulfan, melphalan); the investigator must document in the medical chart that the conditioning regimen is considered to be myeloablative  
or
      - b. TBI (single dose of  $\geq 5$  Gy, or  $\geq 8$  Gy fractionated dose) and at least 1 alkylating agent, and
    - ii. Patient must meet at least 1 of the following criteria (a or b):
      - a. Has at least 1 hepatic-related risk factor, as defined by the European Society for Blood and Marrow Transplantation (EBMT) position statement (adapted and modified from [Mohty et al. 2015](#)), during screening as follows:
        - Transaminase level  $>2.5$  times the upper limit of normal (ULN) during screening or within 14 days prior to screening on a non-screening test if the test was performed as part of patient's routine standard of care
        - Serum total bilirubin level  $>1.5$  times the ULN during screening or within 14 days prior to screening on a non-screening test if the test was performed as part of patient's routine standard of care
        - Prior history of cirrhosis (with biopsy evidence)
        - Prior history of hepatic fibrosis (by histology or other diagnostic scoring system per institutional guidelines)
        - Prior history of viral hepatitis within 1 year before the start of study treatment as indicated by a positive test for any of the following:
          - hepatitis A virus (HAV) immunoglobulin M (IgM) (anti-HAV IgM)

- 
- hepatitis B virus (HBV) core immunoglobulin G (IgG) or IgM (anti-HBc IgG or anti-HBc IgM)
  - HBV surface antigen (HBsAg)
  - HBV DNA by polymerase chain reaction (PCR) or nucleic acid amplification testing (NAAT)
  - Hepatitis C virus (HCV) antibody (anti-HCV) and HCV RNA by PCR or NAAT

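### SAP Table 4 uses one set of vital-sign limits for all ages, so the vital-sign shift table is insensitive to low systolic pressure in adults and misclassifies many young children (minor)

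*SAP*

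**What the plan says.** Protocol 4 enrols adults and children, and inclusion criterion 1 in Protocol 4.1 sets only a lower age bound: "Patient must be above the age of 1 month as of Study Day 1". Protocol 9.14.3 leaves the definition of abnormal vital signs to the SAP, so SAP 11.4 Table 4 is the operative definition.

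Table 4 has one row per parameter. The normal bands are "≥60 and ≤160 mmHg" for systolic pressure, "≥50 and ≤100 mmHg" for diastolic pressure, "≥40 and ≤120 beats per min" for pulse, and 10 to 40 breaths per minute for respiratory rate. The rule that applies these bands makes no reference to age: "Baseline and post-baseline values for each visit in Section 8.4.3 will be categorized as low, normal, or high and presented on a shift table". No vital-sign output is split by age group, although SAP 11.2 and 11.2.1 list adverse-event summaries by age group.

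SAP 11.4 also plans three outputs that do not use Table 4:
- descriptive statistics and change from baseline at each assessment;
- the largest decrease and increase from baseline in systolic and diastolic pressure, included "to assess the potential for defibrotide to cause peri-infusional hypotension";
- a full listing.

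SAP 8.4.3 summarizes the intensive readings around the first two infusions at their nominal times and puts all other readings into the visit windows of SAP 8.4.1.

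**The concern.** What counts as an ordinary pulse, respiratory rate or blood pressure changes a great deal between infancy and adulthood. A single band wide enough to span those ages must be loose for some patients and wrong for others. Here the systolic floor is so low that a large fall in an adult stays inside the band. The pulse ceiling, respiratory ceiling and diastolic floor sit where ordinary infant values may lie.

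Vital signs, including those around infusions, are part of a secondary safety objective (Protocol 2.2, SAP 4.2.2). The shift table is the only planned output that sorts vital signs into low, normal and high. If its categories do not mean the same thing across ages, its counts are hard to interpret.

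A smaller, related point is that the maximum-decrease summary is justified by peri-infusional hypotension, but SAP 11.4 does not confine it to readings taken around an infusion.

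**Working it through.** There is no planned figure to reproduce. The check applies Table 4 as written and then varies the assumptions that the documents do not supply.

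**1. Adults, from Table 4 alone.** Systolic readings of 60, 65, 70, 75, 80, 85 and 89 mmHg all classify as normal; 59 is low. A reading of 60/50 mmHg is normal on both pressure rows. A fall from 120 to 60 mmHg (60/120 = 50%) is a normal-to-normal shift. So is a fall from 160 to 60 mmHg (100/160 = 62.5%).

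The documents give no adult hypotension limit. If it were 80, 85, 90 or 100 mmHg (assumption), the band wrongly called normal would be limit − 60 = 20, 25, 30 or 40 mmHg wide. The problem exists for any adult limit above 60.

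To show the loss of sensitivity, assume adult systolic pressure is normal with mean 120 and SD 15 mmHg, and compare 60 with an illustrative 90. P(low) = Φ((limit − (120 − fall))/15).

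| Mean fall | Limit 60 | Limit 90 |
|---|---|---|
| 20 mmHg | Φ(−2.67) = 0.4% | Φ(−0.67) = 25% |
| 40 mmHg | Φ(−1.33) = 9% | Φ(0.67) = 75% |

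With means of 110 to 130 and SDs of 10 to 20 mmHg, a 40 mmHg fall is flagged in 0.1% to 31% of adults at 60, against 50% to 98% at 90.

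**2. Infants.** All reference ranges here are assumptions. For a range L to U, the share of its width above a ceiling c is (U − c)/(U − L), and the share below a floor f is (f − L)/(U − L).

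| Parameter and Table 4 limit | Assumed ranges | Share labelled abnormal |
|---|---|---|
| Pulse above 120 | 80–140 to 110–170 | 20/60 = 33% to 50/60 = 83% |
| Respiratory rate above 40 | 25–45 to 30–60 | 5/20 = 25% to 20/30 = 67% |
| Diastolic below 50 | 45–65 to 35–55 | 5/20 = 25% to 15/20 = 75% |

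These are shares of range width, not of patients. If infant pulse were normal with mean 130 and SD 15 per minute, P(above 120) = Φ(0.67) = 75% would already be high at baseline. The infant misclassification lies in these three rows; none was identified on the systolic row.

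**3. Maximum decrease.** SAP 11.4 refers to SAP 8.4.3 for the readings used. SAP Table 1 has 11 post-HSCT windows in the prophylaxis phase, and SAP 8.4 takes one value from each (an average if the chosen date has several). Protocol 6.8.3 gives 5 post-start readings for each of 2 infusions: 5 × 2 = 10.

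Assume independent reading noise with SD 10 mmHg. The expected maximum of the falls is ∫₀^∞ (1 − F(x)) dx − ∫₋∞^0 F(x) dx, where F is the product of the normal distribution functions of the individual falls.

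| Readings used | No drug effect | True 10 mmHg infusion fall | Signal kept |
|---|---|---|---|
| 10 infusion readings only | 15.4 | 25.4 | 10.0 |
| 11 windowed + 10 infusion | 18.9 | 25.9 | 7.0 |
| 36 unwindowed daily + 10 infusion | 22.2 | 26.7 | 4.6 |

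The second row follows the SAP's windowing. The third would apply only if every daily reading entered (36 is an assumption). With no drug effect at all, the 11 windowed readings alone give an expected maximum decrease of about 16 mmHg.

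**The case against.** The strongest reply is that Table 4 does not carry the hypotension assessment. SAP 8.4.3 and 11.4 already give change from baseline at 15, 30, 60 and 120 minutes and at 15 minutes after each of the first two infusions. Under SAP 8.2.2, where times were collected, baseline is the last value on or before the time of the first dose, which in the DP arm is the pre-dose reading. A large mean fall would show there, in the maximum decrease and in the listing, and clinical hypotension would be recorded as a graded adverse event. An adult diastolic value below 50 mmHg is still marked low. The limits are the same in both arms, the table is descriptive, and no endpoint or decision rule depends on it. All of this stands, and it is why the point is minor.

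Three stronger readings are therefore not supported:
- A reader might infer that the report could miss a hypotension signal. The outputs above do not use Table 4, so it would not go unseen for this reason.
- A reader might infer that no shift can be seen in infants. Even if 75% start high on pulse, 25% do not, and high-to-normal shifts remain visible.
- A reader might infer that the maximum decrease cannot separate infusion-related falls from others. Under the SAP's windowing it keeps about 7 of 10 mmHg.

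The reply does not rescue the table itself. Its categories still fit neither adults on the systolic row nor infants on three others.

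**Conclusion.** The point holds as a minor one. That a single set of limits covers everyone from above 1 month of age, and that systolic 60 to 89 mmHg counts as normal in adults, is plain from the text. That this misses adult hypotension assumes only a limit above 60 mmHg. The infant misclassification rests on assumed reference ranges, but it follows for any infant upper pulse limit above 120, upper respiratory limit above 40 or lower diastolic limit below 50. Its overall weight is unknown, because the documents do not give the share of infants.

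The consequence is an insensitive and partly misclassified descriptive safety table. The maximum decrease, which has no infusion window, is diluted but not invalid: about 30% of a 10 mmHg effect is lost under the windowing and noise assumptions above. Efficacy analyses are untouched.

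**What to change.** - Replace Table 4 with age-banded limits pre-specified from a cited reference, assigned by age at baseline. No particular limits are proposed here.
- Have the sponsor confirm whether the 60 mmHg systolic limit was meant to apply to adults.
- Add a per-patient maximum fall in systolic and diastolic pressure, measured from the pre-dose reading and restricted to the readings of infusions 1 and 2. Keep the existing maximum decrease and increase as the general summary.

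Age and all these readings are already collected, so only SAP text and programming change. The price is more rows in the shift table and one more summary.
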